10.2.5 Treatment-induced Anti-MENOPUR Antibodies

The proportion of subjects with treatment-induced anti-MENOPUR antibodies as well as the proportion of subjects with treatment-induced anti-MENOPUR antibodies with neutralizing capacity will be tabulated. Within each treatment group, a 95% Clopper-Pearson confidence interval will be constructed for both the proportion of subjects with treatment-induced anti-MENOPUR antibodies and for the proportion of subjects with treatment-induced anti-MENOPUR antibodies with neutralizing capacity.

10.2.6 Technical Malfunction of the Pen

The frequency of reported malfunctions of the administration pen will be presented in a summary table.

10.2.7 Vital Signs

The baseline for the vital sign analyses will be calculated as described in Section 1.1.1.

10.2.7.1 Summary Statistics

Mean change from baseline at each time point will be presented for each vital sign variable using the process outlined in Section 1.2.1.

10.2.7.2 Changes Relative to Normal Range

Each vital sign variable value is classified as either 'Low', 'Normal', or 'High'. Shift tables will be prepared to show the number and percentage of subjects that experience a shift from baseline to the end-of-stimulation visit and from baseline to the end-of-trial visit.

10.2.7.3 Markedly Abnormal Changes

Summary tables will be prepared displaying the proportion of subjects who have at least one markedly abnormal value. The table will also include a break-down by classification of the baseline value. Markedly abnormal criteria for vital signs are specified in Appendix 2.

10.2.7.4 Data Listings

Data listings will be prepared by treatment group, center, subject number, and time point for all vital sign values (including screening and baseline) and abnormal values will be flagged.

10.2.8 Physical Examination

Physical examination at the end-of-trial visit will be compared to baseline (as defined in Section 1.1.1) and summarized in shift tables. All subjects with any abnormal finding will be listed per subject.

10.2.9 Gynecological Examination

Gynecological examination at the end-of-trial visit will be compared to baseline (as defined in Section 1.1.1) and summarized in shift tables. All subjects with any abnormal finding will be listed per subject.

10.2.10 Safety Laboratory Variables

The baseline for the safety laboratory variable analyses will be calculated as described in Section 1.1.1.

10.2.10.1 Summary Statistics

The circulating levels of clinical chemistry and hematology parameters, including change from baseline, will be tabulated for each time point for each laboratory variable. Mean change from baseline to the end-of-stimulation visit and to the end-of-trial visit will be presented for each laboratory variable using the process outlined in Section 1.2.1.

10.2.10.2 Changes Relative to Normal Range

Each safety laboratory variable value is classified as either 'Low', 'Normal', or 'High'. Shift tables will be prepared to show the number and percentage of subjects that experience a shift from baseline to the end-of-stimulation visit and from baseline to the end-of-trial visit.

10.2.10.3 Markedly Abnormal Changes

Summary tables will be prepared displaying the proportion of subjects who have at least one markedly abnormal value. The table will also include a break-down by classification of the baseline value. Markedly abnormal criteria for the clinical chemistry and hematology variables are specified in Appendix 2.

10.2.10.4 Data Listings

Data listings will be prepared by treatment group, center, subject number, and time point for all safety laboratory values (including screening) and abnormal values will be flagged along with their determination of clinically significant or not clinically significant. Laboratory variables will be grouped under "Hematology" and "Clinical Chemistry".

11 **Post-trial Assessments**

The post-trial assessments will be reported as an addendum to the 000303 clinical study report.

11.1 Live Birth Rate

The live birth rate will be presented by treatment group and analyzed using the method described for secondary pregnancy endpoints in Section 9.1.2. Subjects with no information on live birth will be defaulted to a negative response.

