9.8 Safety

9.8.1 General Considerations

Analyses for the safety analysis set will be conducted according to the actual treatment received.

Missing values will be treated as missing, except for causality, intensity, seriousness, and outcome of adverse events. A worst-case approach will be used: if causality is missing, the adverse event will be regarded as related to the IMP; if the intensity of an adverse event is missing, the adverse event will be regarded as severe; if seriousness is missing, the adverse event will be regarded as serious; if outcome is missing, and no date of outcome is present, the outcome is regarded as 'ongoing'.

Data will be presented by summary tables and listings only. Categorical data will be summarized by treatment using the number and percentage of subjects in each category. For calculation of percentages, the denominator will be the total number of subjects in the respective treatment group in the safety analysis set. Continuous data will be summarized by treatment using number, mean, standard deviation, median, minimum, and maximum.

All individual subject data will be listed per subject and treatment as observed including any derived values.

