9.8.11 Additional Endpoints

All post-trial endpoints will be summarized using tables and figures, as appropriate. Additional details will be specified in the separate Statistical Analysis Plan for the post-trial endpoints. The post-trial endpoints include:

• Live birth rate

Trial Code: 000303 Date: 14 Oct 2019 E-Study Protocol-21539; Ver. 6.0 Supersedes: 5.0

Page 88 of 103

- Late pregnancy loss rate (defined as an ongoing pregnancy but no live birth).
- Neonatal health including SAEs at birth, and SAEs at 4 weeks and minimum 6 months after birth.

Descriptive statistics will be provided in each of the respective post-trial endpoints.

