10 DATA HANDLING

10.1 Source Data and Source Documents

Source Data – ICH Definition

Source data are defined as all information in original records and certified copies of original records of clinical findings, observations, or other activities in a clinical trial necessary for the reconstruction and evaluation of the trial. Source data are contained in source documents (original records or certified copies).

Source Documents - ICH Definition

Source documents are defined as original documents, data, and records (e.g. hospital records, clinical and office charts, laboratory notes, memoranda, subjects' diaries or evaluation checklists, pharmacy dispensing records, recorded data from automated instruments, copies or transcriptions certified after verification as being accurate copies, microfiches, photographic negatives, microfilm or magnetic media, x-rays, subject files, and records kept at the pharmacy, at the laboratories and at medico-technical departments involved in the clinical trial).

Trial-specific Source Data Requirements - Ferring

Source documents need to be preserved for the maximum period of time permitted by local requirements. For each subject enrolled, the investigator will indicate in the source documents that the subject participates in this trial, and will record at least the following information, if applicable:

- Existence of subject (initials, date of birth)
- Confirmation of participation in trial (trial ID, subject ID)
- Informed consent (date and time of obtaining written informed consent)
- Eligibility for participation in the trial (documenting all inclusion / exclusion criteria)
- Relevant medical history, infertility history, menstrual history and reproductive history
- Body weight measurements
- Visit dates
- Dates of administration of IMP
- Dates and daily doses of NIMP
- Dates and daily doses of concomitant medication
- Date of oocyte retrieval and number of oocytes retrieved
- Date of transfer and number and quality of blastocysts transferred
- Number and quality of blastocysts cryopreserved

Supersedes: 5.0 Page 90 of 103

- Results of βhCG test and ultrasound at clinical and ongoing pregnancy visits
- Pregnancy outcome, i.e. live birth or pregnancy loss, and neonatal health at birth
- Injection site reactions after IMP administration diary
- Adverse events (description as well as start/stop date and time)
- OHSS symptoms, preventive interventions, investigations and treatments

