10.2.3 Early Pregnancy Loss

Early pregnancy loss is defined as a positive β hCG test but no ongoing pregnancy at 8-9 weeks after blastocyst transfer. The early pregnancy loss rate will be presented by treatment group. The denominator for the early pregnancy loss rate consists of those subjects with a positive β hCG.

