11.2 Late Pregnancy Loss

Late pregnancy loss is defined as an ongoing pregnancy but no live birth. The rate of late pregnancy loss will be presented by treatment group.

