11.3 Neonatal Health

The gestational age, gender, weight, length, and Apgar scores (1 minute, 5 minutes, and 10 minutes) will be presented by treatment group. Furthermore, admissions to care units (NICU, NCU, or PCU), admissions to care units for longer than 2 hours, malformations or congenital anomalies, neonatal death, and important medical events will be presented by treatment group at birth, at 4 weeks after live birth, and after 6 months following live birth.

Neonatal SAEs will be summarized from birth through a minimum of 6 months after birth. Written narratives will be issued for all SAEs.

Parameters relating to maternal health will also be presented by treatment group. These will include clinically relevant pregnancy, labor, or delivery complications, COVID-19 infection, exposure to risk factors of congenital anomalies or malformations, and maternal death in connection with pregnancy or labor.

12 Interim analyses

A sample size reassessment will be performed without breaking the blind and without meaningful inflation of the Type I error of the trial (see Appendix 1), in line with the current regulatory guidelines for non-inferiority trials by the Food and Drug Administration (FDA). The one-sample standard deviation of the primary efficacy endpoint will be evaluated in a blinded manner in relation to the assumptions underlying the sample size calculation.

The sample size reassessment is to take place when 70% of the planned sample size has provided a primary endpoint (280 primary endpoints) or when 300 subjects have been randomized, whichever occurs first.

A restricted recalculation rule for the sample size reassessment will be used. The trial will originally target 400 randomized subjects. At the time of the interim analysis, the estimated one-sample standard deviation will be used to recalculate the required sample size. If the recalculated sample size is less than 400, then the targeted sample size will remain at 400 (i.e.; the sample size will never decrease below 400). If the recalculated sample size is greater than 400, however, then the targeted sample size will be increased to either the recalculated sample size or 500, whichever is smaller.

13 Deviations from the protocol

There is one deviation from the planned analysis in the protocol. Center will be incorporated into statistical analyses as a fixed effect instead of a random effect.

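### Does the negative default for unknown live birth turn unknown outcomes into late pregnancy losses?

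*SAP*

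**What the plan says.** SAP 11.1 (Live Birth Rate) presents and analyzes live birth by arm and adds: "Subjects with no information on live birth will be defaulted to a negative response". SAP 11.2 follows: "Late pregnancy loss is defined as an ongoing pregnancy but no live birth". Its only other sentence says that the rate is shown by treatment group. It names no denominator, no analysis set and no handling of an ongoing pregnancy whose outcome is unknown.

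Four other places bear on the point:

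- SAP 10.2.3, on early loss, does fix a denominator: "The denominator for the early pregnancy loss rate consists of those subjects" with a positive βhCG.
- Protocol 9.8.1 says for safety data: "Missing values will be treated as missing, except for causality, intensity, seriousness, and outcome of adverse events". It also says: "For calculation of percentages, the denominator will be the total number of subjects in the respective treatment group in the safety analysis set". Late loss is listed at protocol 9.8.11, inside the same section 9.8, but 9.8.11 leaves the detail to a SAP for the post-trial endpoints.
- Protocol 8.4.4 sets the terminology: a late loss is a pregnancy loss that occurs once ongoing pregnancy has been reached, during post-trial follow-up.
- SAP section 13 says: "There is one deviation from the planned analysis in the protocol". That one concerns center as a fixed rather than a random effect.

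**The concern.** Setting an unknown live birth to negative is conservative for the live birth rate. Used for a harm outcome, the same value works the other way. If a programmer derives one live birth variable under 11.1 and reuses it in 11.2, each ongoing pregnancy with unknown outcome meets the definition of late loss, and the table reports a loss that nobody observed. When documented losses are few, a handful of unknown outcomes could outnumber them.

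The missing denominator adds a second uncertainty. Protocol 9.8.1 would give the whole safety set, whereas the pattern of SAP 10.2.3 would give the subjects at risk. Counting unknowns as losses would also sit badly with the protocol rule that missing safety values stay missing, and SAP section 13 declares no such departure. What is at stake is the accuracy of one descriptive rate in the addendum.

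**Working it through.** **Which reading the text supports**

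1. *Position of the default.* The sentence is in 11.1 and nothing in 11.2 refers back to it. The SAP writes such rules separately for each endpoint: 9.3.1 (βhCG), 9.3.2 (clinical pregnancy), 9.3.6 (oocytes retrieved), 9.3.7 (oocyte maturity) and 9.3.9 (blastocysts). The ordinary reading is that each rule governs its own subsection.
2. *Nature of the endpoint.* Protocol 8.4.4 describes late loss as an event, and protocol 7.4.2 speaks of its occurrence. The gloss in both places repeats the absence of a live birth, so the wording is not watertight. Even so, a subject whose outcome nobody knows has not been shown to have had a loss.
3. *Data to count.* Protocol 10.1 requires the source documents to hold "Pregnancy outcome, i.e. live birth or pregnancy loss, and neonatal health at birth". Documented losses can therefore be told apart from unknown outcomes. Stillbirths are in addition recorded as serious adverse events under protocol 8.5.1, which gives a cross-check on part of the count.
4. *Denominator.* Protocol 7.4.1 follows every subject with an ongoing pregnancy, which is the group at risk. The parallel to SAP 10.2.3 is all ongoing pregnancies, because 10.2.3 keeps every subject with a positive βhCG and drops none for an unknown later outcome. The number of ongoing pregnancies per arm is reported under SAP 9.3.3, so a reader can convert from one denominator to another.
5. *Section 13.* Its silence settles nothing. The 11.1 default already replaces a missing value for another endpoint listed in protocol 9.8.11 and is not listed there either.
6. *How unknowns arise.* Protocol 14.5 requires consent to neonatal data collection before randomization, so refusal at the outset is largely closed off. Later withdrawal of consent and loss to follow-up remain possible.

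**How much the reading could matter**

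The plan states no figure for late loss, so there is none to reproduce and every input below is an assumption except the planned 400 subjects. Let p be the true loss rate among ongoing pregnancies and m the share with unknown outcome, independent of the true outcome. If unknowns count as losses,

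reported rate = p + m(1 − p).

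| p | m = 2% | m = 5% | m = 10% |
|---|---|---|---|
| 1% | 3.0% | 6.0% | 10.9% |
| 2% | 4.0% | 6.9% | 11.8% |
| 3% | 4.9% | 7.9% | 12.7% |

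For example, 0.02 + 0.05 × 0.98 = 0.069. False losses equal true ones at m = p/(1 − p), which is 0.02/0.98 = 2.0% for p = 2%.

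Take both arms together with 400 treated, 160 ongoing pregnancies, 3 documented losses and 8 unknown outcomes:

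| Numerator | Denominator | Rate |
|---|---|---|
| documented losses | ongoing pregnancies | 3/160 = 1.9% |
| documented losses | known outcomes | 3/(160 − 8) = 3/152 = 2.0% |
| documented losses | all treated | 3/400 = 0.75% |
| losses plus unknowns | ongoing pregnancies | (3 + 8)/160 = 11/160 = 6.9% |
| losses plus unknowns | all treated | 11/400 = 2.75% |

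The first two rows show that dropping the unknowns from the denominator hardly matters. The numerator matters far more. For one arm of 200, with 50 to 90 ongoing pregnancies, 1 to 2 losses and 1 to 6 unknowns, documented losses over ongoing pregnancies run from 1/90 = 1.1% to 2/50 = 4.0%. With unknowns added to the numerator they run from 2/90 = 2.2% to 8/50 = 16.0%. With no unknowns the missing-data question disappears.

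**The case for a change.** The best case for a change is that nothing forbids the wrong reading. The two subsections are adjacent and use the same live birth status. The SAP rule that missing safety values stay missing is in section 10 and is not extended to section 11. The SAP spells out rules for many other endpoints, and for early loss it spells out the denominator, so the silence in 11.2 is noticeable. Protocol section 9 foresees a separate post-trial SAP, but none is among the documents, and the SAP's change history says that version 2.0 itself added the post-trial detail. One clause would remove the doubt.

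This stands as a description of the text: 11.2 is incomplete, and a literal programmer could produce the higher figures shown above. It does not show that the plan prescribes them. The reading requires carrying a rule out of its own subsection and treating an unknown as an observed event, against the sense of protocol 8.4.4. The supposed undeclared departure from protocol 9.8.1 depends on that carry-over, and on 9.8.1 binding an endpoint whose detail the protocol hands to the SAP. Neither is established. The table shells, which SAP section 14 places in a separate document, may also fix the denominator.

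**Conclusion.** No change is called for. SAP 11.2 leaves out detail that an analyst would fill sensibly: count documented late losses over subjects with an ongoing pregnancy, and report how many outcomes are unknown. No rule in the plan gives a wrong result as it stands.

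The size cannot be read from the documents, which give no late-loss rate, no number of ongoing pregnancies and no share of unknown outcomes. On the assumed totals the two readings give 1.9% and 6.9%, and they coincide if every outcome is known. Even the wrong reading would overstate a harm rather than hide one. It would create a difference between arms only if unknown outcomes were unevenly spread; nothing in the documents suggests that, and protocol 3.5.1 keeps the blind through the post-trial activities. Late loss is untested and descriptive, and SAP section 11 puts it in an addendum, so the primary analysis of fertilized oocytes does not depend on it.

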11.2 Late Pregnancy Loss

Late pregnancy loss is defined as an ongoing pregnancy but no live birth. The rate of late pregnancy loss will be presented by treatment group.

11.3 Neonatal Health

The gestational age, gender, weight, length, and Apgar scores (1 minute, 5 minutes, and 10 minutes) will be presented by treatment group. Furthermore, admissions to care units (NICU, NCU, or PCU), admissions to care units for longer than 2 hours, malformations or congenital anomalies, neonatal death, and important medical events will be presented by treatment group at birth, at 4 weeks after live birth, and after 6 months following live birth.

Neonatal SAEs will be summarized from birth through a minimum of 6 months after birth. Written narratives will be issued for all SAEs.

Parameters relating to maternal health will also be presented by treatment group. These will include clinically relevant pregnancy, labor, or delivery complications, COVID-19 infection, exposure to risk factors of congenital anomalies or malformations, and maternal death in connection with pregnancy or labor.

12 Interim analyses

A sample size reassessment will be performed without breaking the blind and without meaningful inflation of the Type I error of the trial (see Appendix 1), in line with the current regulatory guidelines for non-inferiority trials by the Food and Drug Administration (FDA). The one-sample standard deviation of the primary efficacy endpoint will be evaluated in a blinded manner in relation to the assumptions underlying the sample size calculation.

The sample size reassessment is to take place when 70% of the planned sample size has provided a primary endpoint (280 primary endpoints) or when 300 subjects have been randomized, whichever occurs first.

A restricted recalculation rule for the sample size reassessment will be used. The trial will originally target 400 randomized subjects. At the time of the interim analysis, the estimated one-sample standard deviation will be used to recalculate the required sample size. If the recalculated sample size is less than 400, then the targeted sample size will remain at 400 (i.e.; the sample size will never decrease below 400). If the recalculated sample size is greater than 400, however, then the targeted sample size will be increased to either the recalculated sample size or 500, whichever is smaller.

13 Deviations from the protocol

There is one deviation from the planned analysis in the protocol. Center will be incorporated into statistical analyses as a fixed effect instead of a random effect.

Because randomization is stratified by age strata and center, it was planned in the protocol to perform analyses by adjusting for both age strata and center. Age strata was to be incorporated as a fixed effect and center was to be incorporated as a random effect.

In this statistical analysis plan, however, we incorporate center as a fixed effect. The reason for doing so is twofold. First, centers are rarely chosen at random. Second, the interpretation of an interaction between center and any other variable of interest would be complicated by the use of a random effect. Interactions between fixed effects are much more readily interpretable. While there are no pre-planned analyses that incorporate an interaction that includes center, it is possible that a post-hoc analysis could.

14 Tables, Listings and Figures

Tables, listings, and figures (TLF) will be presented in a separate document.

15 References

1. Rubin, D.B. (1987) Multiple imputation for nonresponse in surveys. New York: John Wiley & Sons.

Appendix 1

Assessment of Type I Error Inflation

In November 2019, the FDA released a guidance for industry document titled, "Adaptive Designs for Clinical Trials of Drugs and Biologics." Of relevance for the present trial, Section IV: Adaptive Designs Based on Non-Comparative Data states, "These adaptations generally do not inflate the Type I error probability. However, there is the potential for limited Type I error probability inflation in trials incorporating hypothesis tests of non-inferiority or equivalence (Friede and Kieser 2003). Sponsors should evaluate the extent of inflation in these scenarios." The present trial is a non-inferiority study that includes a form of non-comparative adaptive design, namely a blinded sample size recalculation.

Using the methods described in Appendix 1 of Friede and Kieser (2003), a simulation study was performed. The simulation study assessed the potential Type I error of the present trial given the design considerations for the sample size recalculation (See Section 3.2). The 'true' pooled standard deviation was set to range from 3.0 to 15.0 using increments of 0.1. For each increment, 10,000,000 simulations were performed. Based upon the design considerations of the present trial, the minimum sample size was set to 400, the maximum sample size was set to 500, and the sample size recruited at the time of the sample size recalculation was set to 280. Likewise, when recalculating the sample size during each simulation rep, an alternative treatment difference of 0 was assumed, the non-inferiority margin was set to -1.6, a two-sided alpha of 0.05 was used, and the power was set to 85%.

The results of the simulation can be seen in Figure 0-1 below. For true pooled standard deviations that are less than 5 and greater than 6, the Type I error is well controlled. For true pooled standard deviations between 5 and 6, there is a small amount of Type I error inflation. The maximum Type I error observed was 0.0253705, which occurred at a true pooled standard deviation of 5.6.

Figure 0-1: Actual Type I error of the 000303 trial given the true pooled standard deviation.

One conservative method for controlling the maximum Type I error inflation was illustrated by Friede and Stammer (2010). An iterative procedure is performed, adjusting alpha until the maximum observed Type I error is within a certain distance, epsilon, of the predefined desirable level of Type I error. This method was applied to the present trial by setting epsilon equal to 0.0001 (i.e.; a maximum Type I error no greater than 0.0251).

The results of applying the procedure can be seen in Figure 0-2 below. When adjusting the onesided Type I error from 0.025 to 0.0246 (or, equivalently, the two-sided Type I error from 0.05 to 0.0492), the maximum observed Type I error is within 0.0001 of the pre-specified Type I error of 0.025. The maximum observed Type I error was 0.0250291 and again occurred at a standard deviation of 5.6.

Figure 0-2: Adjusted Type I error after applying an alpha correction.

The Type I error inflation observed in Figure 0-1 is considered to be small and inconsequential. Therefore, no adjustments to the primary analysis are taken. A sensitivity analysis, however, is added. As described in Section 9.2.2, the primary analysis will be repeated using the same analysis set and imputation approach, but a different alpha level when constructing the two-sided confidence interval. Instead of a two-sided 95% confidence interval, a two-sided 95.08% confidence interval will be constructed. This confidence interval reflects the adjustment necessary to contain the maximum Type I error to be within 0.0001 of the pre-specified desired level of Type I error.

Below are the references made in the appendix.

- 1. Friede, T. & Kieser, M. (2003) Blinded sample size reassessment in non-inferiority and equivalence trials. *Statistics in Medicine*, 22:995-1007. DOI: 10.102/sim.1456.
- 2. Friede, T. & Stammer, H. (2010) Blinded sample size recalculation in noninferiority trials: A case study in dermatology. *Drug Information Journal*, 44:598-608.

Ferring Pharmaceuticals

Appendix 2

Variable Code	Variable	Units	Low	High
RBC	Erythocytes	10^12/L	< 3.0	N.A
WBC	Leukocytes	10^9/L	< 2.5	> 15.0
HGB	Haemoglobin	g/L	< 100	> 190
НСТ	Haematocrit	RATIO	< 0.28	> 0.5
EOSLE	Eosinophils/Leukocytes	%	N.A	≥ 10
NEUTLE	Neutrophils/Leukocytes	%	≤15	≥ 90
LYMLE	Lymphocytes/Leukocytes	%	≤10	≥ 80
MONOLE	Monocytes/Leukocytes	%	N.A	≥20
BASOLE	Basophils	%	N.A	≥ 5
PLAT	Platelets	10^9/L	< 110	> 600
AST	AST	IU/L	N.A	> 3xULN
BUN	Blood urea nitrogen	mmol/L	N.A	> 12.5
CA	Calcium	mmol/L	< 1.75	> 2.74
CL	Chloride	mmol/L	N.A	N.A
ALT	ALT	IU/L	N.A	> 3xULN
CREAT	Creatinine	umol/L	N.A	> 3xULN
GGT	GGT	IU/L	N.A	> 3xULN
GLUC	Glucose	mmol/L	< 2.5	> 16.7
K	Potassium	mmol/L	< 3.0	> 5.8
SODIUM	Sodium	mmol/L	< 125	> 155
ALP	Alkaline phosphatase	IU/L	N.A	$> 3 \mathrm{xULN}$
LH	Luteinizing hormone	IU/L	N.A	>10

Table 1Markedly Abnormal Criteria for Laboratory Tests

Table 2	Markedly	Abnormal	Criteria	for V	Vital Signs	*
1 a 0 10 2	wiarkeury	Automat	Cincina	101	v nai oigiid	,

Variable	Criterion Value	Change from Baseline
Systolic blood pressure	\geq 180 mmHg \leq 90 mmHg	Increase of $\ge 20 \text{ mmHg}$ Decrease of $\ge 20 \text{ mmHg}$
Diastolic blood pressure	\geq 105 mmHg \leq 50 mmHg	Increase of ≥ 15 mmHg Decrease of ≥ 15 mmHg
Pulse	≥ 120 bpm ≤ 50 bpm	Increase of ≥ 15 bpm Decrease of ≥ 15 bpm

* To be identified as markedly abnormal, a treatment value must meet the criterion value and also the specified change from baseline.
